#### 7.5.1 Unscheduled Visits

An unscheduled visit is any visit to the clinical site (other than those specified in the protocol), during which the subject has a complaint regarding the study eye or study eye treatment is required. No specific testing is required at unscheduled visits.

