# 9.2 Postoperative Adverse Events

- Chronic pain in the study eye present at 3 months postoperatively or later
- Flat anterior chamber with lens/cornea touch
- Shallow chamber with peripheral iridocorneal apposition
- BCVA loss of 3 Snellen lines compared to baseline at 3 months postoperatively or later
- Hypotony (defined as IOP < 6 mmHg) at 1 month postoperatively or later
- Maculopathy
- Hypotonic maculopathy
- CyPass obstruction causing an untoward effect in the study eye
- CyPass malposition
- CyPass migration, causing an untoward effect in the study eye
- Wound dehiscence
- Persistent anterior chamber cell and flare requiring steroid treatment after 2 months postoperatively
- Endophthalmitis
- Cataract formation or progression outside of expected progression
- Persistent hyphema present at 1 week postoperatively or later
- Corneal opacification, or corneal decompensation
- Significant corneal edema
- Retinal complications (dialysis, flap tears, retinal detachment, or proliferative vitreoretinopathy)

- Choroidal hemorrhage or choroidal effusion, defined as a choroidal effusion or detachment with at least a partially hemorrhagic component that obstructs vision or causes pain (including both peripheral and "kissing" choroidal detachments) lasting longer than 1 month
- Significant elevation in IOP requiring non-medical intervention
- Other events resulting in unplanned ocular surgical reintervention (other than paracentesis to relieve pressure prior to 1 week postoperative or Nd:YAG laser procedure for treatment of posterior capsular opacification)
- Loss of eye
- Significant ptosis
- Atrophy/phthisis
- Significant foreign body sensation at or after 3 months postoperative
- Increase in C:D ratio of  $\geq 0.3$  units on slit lamp biomicroscopic examination
- Confirmed increase in visual field loss outside of expected progression

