3.1 General Reporting Conventions

- Only one eye per subject may be treated under the study protocol. If both eyes qualify
 for the study, the study investigator will choose which eye will be the study eye.
 Unless specified otherwise, all ocular results refer to the study eye only. Therefore,
 throughout this SAP and corresponding tables and data listings, the number of
 subjects and eyes are synonymous.
- Available data at each assessment time point will be presented. No imputations will be made for missing data.

Document: TDOC-0053376 Version: 2.0; Most-Recent; Effective; CURRENT

Status: Effective

- Appropriate descriptive statistics will be computed and displayed by assessment time point for both continuous and categorical variables. For continuous variables, descriptive statistics include n (number of subjects/eyes) with non-missing data, mean, standard deviation (SD), median, minimum and maximum values. For categorical parameters, the number and percentage of subjects/eyes within each category will be presented. The denominator for percentages will be based on the number of subjects with non-missing data appropriate for summary purposes. Unless otherwise noted, percentages will be presented to one decimal place. Any confidence intervals (CI) will be at the alpha = 0.05 (two-sided) level.
- Summary tables will be presented by treatment and overall, as appropriate, for both phases/cohorts combined.
- Study day: Study day will be calculated relative to the date of stent implantation surgery (Day 0) as: Date of event – date of surgery. This formula will be used when calculating days to a specific event (i.e., ocular medications and/or AE start date). A negative study day indicates an event prior to surgery.
- Individual data listings of select data represented on the eCRF will be provided to facilitate investigation of the tabulated values and to allow for clinical review of key variables. All data listings will be sorted by Treatment (i.e., CyPass, CyPass with 30 μl, and CyPass with 60 μl), Cohort (1 or 2), site-subject number, visit, and assessment time points where appropriate. Data from unscheduled visits will be excluded from the summary tables (except for adverse events) but included, chronologically, in the data listings.
- Analyses will be generated using SAS® version 9.2 or higher.

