6.3.3 Best Corrected Visual Acuity (BCVA)

The number and percentage of responses relative to each Snellen equivalent category (i.e., 20/20 or better, 20/25 or better, etc.) will be presented at each assessment visit. Results will also be included in the data listings.

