6.3.4 Intraocular Pressure

Intraocular pressure (IOP) measurements will be recorded in mmHg and reported up to one decimal place. IOP measurements will be summarized relative to both medicated and unmedicated baseline assessments compared to postoperative visits as follows. For medicated baseline IOP, descriptive summaries of observed values, as well as change and percent change from medicated baseline (Baseline1) values will be presented at each postoperative assessment visit compared to medicated baseline. Similarly, descriptive

Document: TDOC-0053376 Version: 2.0; Most-Recent; Effective; CURRENT

Status: Effective

summaries of observed values, as well as change and percent change from unmedicated baseline (Baseline2) values will be presented at each postoperative assessment visit compared to unmedicated baseline.

Further, IOP measurements over time at the Screening, Baseline, 1 Mo, 3 Mos, 6 Mos, 12 Mos, and 12 Mos unmedicated assessments will be presented graphically using side-by-side box plots to compare results between the CyPass alone and CyPass with 60 µL groups.

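### The visible SAP derives no count of eyes losing 3 Snellen lines or of eyes with low IOP from the measurements, so both rest on adverse event reporting in an unmasked study

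*SAP*

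**What the plan says.** **Unscheduled visits.** SAP 3.1 states: "Data from unscheduled visits will be excluded from the summary tables (except for adverse events". The same sentence keeps these data, "included, chronologically, in the data listings". Protocol 7.5.1 defines an unscheduled visit as one outside the protocol schedule "during which the subject has a complaint regarding the study eye or study eye treatment is required", and adds: "No specific testing is required at unscheduled visits".

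**BCVA.** SAP 6.3.3 plans "The number and percentage of responses relative to each Snellen equivalent category" at each visit, in cumulative form (20/20 or better, 20/25 or better, and so on), plus listings. It mentions no change from baseline and no lines lost. Protocol 9.2 lists a loss of 3 Snellen lines against baseline, from 3 months after surgery, as an anticipated adverse event.

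**IOP.** SAP 6.3.4 plans observed values, change and percent change from both the medicated and the unmedicated baseline at each postoperative visit. SAP 3.1 adds minimum and maximum for all continuous variables. The box plots cover "IOP measurements over time at the Screening, Baseline, 1 Mo, 3 Mos, 6 Mos, 12 Mos, and 12 Mos unmedicated assessments". Protocol 9.2 names "Hypotony (defined as IOP < 6 mmHg) at 1 month postoperatively or later" and "Significant elevation in IOP requiring non-medical intervention" as anticipated adverse events.

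**Adverse events.** The text that opens protocol section 9 requires every study-eye adverse event to be reported and says the anticipated list is not exhaustive. SAP 6.3.1 counts ocular events by group and coded term. SAP 1.4 says the study was not masked.

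**The concern.** The comparison of interest is stent implantation with and without viscoelastic placed in the eye at surgery. Low pressure and loss of vision are natural safety questions for that comparison, and safety is half of the stated objective (SAP 1.1). A reader of the final tables will want to know how many eyes in each arm lost 3 lines and how many had low pressure. The visible SAP answers neither from the measurements. Both answers depend on whether an investigator who may know the treatment recorded an adverse event. Moreover, readings from visits prompted by a complaint or a need for treatment, where an abnormal value is more likely, enter no BCVA or IOP table. The stake is the completeness and objectivity of the safety comparison; the efficacy result is not affected.

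**Working it through.** The plan states no figure on this point, so there is none to reproduce. The check sets the passages side by side, with a little arithmetic.

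**1. Can the BCVA table hide a 3-line loss?** Let N(c) be the number of eyes at Snellen category c or better. Between baseline and a later visit, let L(c) eyes fall below c and G(c) eyes rise to c or better. Among eyes measured at both visits, the change in the table is

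change in N(c) = G(c) − L(c).

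Only the difference is visible. If one eye drops three lines from category a to category b and another rises from b to a, then at every threshold crossed the change is 1 − 1 = 0, and at every other threshold it is 0. The table is identical, yet one eye has met the protocol's criterion. Exact cancellation is not needed for the problem to exist; any gains reduce the visible loss.

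**2. Does the SAP derive within-eye loss elsewhere?** It does for visual field. SAP 6.3.7 classifies each eye's change from screening at 6.0 dB. The opening of SAP section 3 says changes from baseline will be assessed where appropriate, and SAP 3.2 defines the single Baseline that BCVA would use. The machinery exists, but it is not applied to acuity, where the protocol itself supplies the threshold.

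**3. Do the IOP summaries count eyes with low pressure?** A minimum below a cut shows that at least one eye was below it at that visit. It does not show how many, or whether low minima at two visits belong to the same eye. Mean, SD and median do not give the count either.

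**4. What reaches which output?**

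| Finding | By-visit table, scheduled visits | Seen only at an unscheduled visit | Named in protocol 9.2 |
|---|---|---|---|
| 3-line BCVA loss | Not derived | Listing only | From 3 months |
| Low IOP before 1 month | Minimum only, no count | Listing only | No |
| Low IOP from 1 month | Minimum only, no count | Listing only | Yes, < 6 mmHg |
| High IOP | Maximum only, no count | Listing only | Only if non-medical intervention is needed |

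Any of these enters the adverse event tables if it is reported as an event, whichever visit it came from.

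**5. Which cuts do the documents supply?** For hypotony, protocol 3.2 uses IOP < 5 mmHg when describing cyclodialysis clefts and protocol 9.2 uses < 6 mmHg. The two passages differ and must be reconciled. For high IOP after surgery there is no mmHg limit. The figure > 36 mmHg in protocol 7.1 governs exit during preoperative washout only.

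**The case against.** The case against is substantial, and most of it stands.

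- IOP is well covered at scheduled visits: within-eye change and percent change from two baselines, with extremes shown.
- Day 1, Week 1 and Month 1 are scheduled visits (protocol 2.6), so the unscheduled-visit rule does not remove their readings. Only the box plots omit Day 1 and Week 1.
- Adverse events are exempt from the exclusion, must all be reported for the study eye, and are counted by term. Because the anticipated list is open-ended, early hypotony or a medically treated pressure rise can still be an adverse event.
- Keeping irregular readings out of by-visit means is sound practice. No testing is required at those visits, so a reading may not exist.
- SAP 6.2 sets no safety hypotheses; the safety analysis is descriptive.
- The SAP is based on protocol Version F, while the protocol at hand is Version D. Parts of the SAP are not visible, so further summaries may exist.

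A reader might infer that the plan leaves early hypotony, pressure spikes and vision loss uncounted, that IOP is reported only cross-sectionally, or that the protocol sets limits which the SAP ignores for all three. The documents do not support this. IOP change is planned, adverse events are counted wherever found, the named hypotony term begins at 1 month, and no postoperative spike limit exists.

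The objection does not remove two facts: BCVA loss within an eye is never derived from the measurements in the visible text, and no visible table counts eyes with low IOP.

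**Conclusion.** The point holds in a limited form. In the visible SAP, the protocol's 3-line criterion is counted only through investigator reporting in an unmasked study, and the number of eyes with low IOP is not derived at all. Readings from unscheduled visits can inform either question only through the listings or through a reported adverse event. The BCVA part is the stronger, because the protocol gives the threshold and the SAP already uses the same kind of table for visual field.

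No numerical size can be given: the documents contain no rates of unscheduled visits, low IOP or line loss. The effect is confined to descriptive safety reporting and leaves the primary endpoint and its power unchanged. The conclusion assumes that the parts of the SAP not shown contain no such tables and that Version F did not alter the protocol 9.2 definitions. It does not assume that investigators under-report; the counts are worth having because they would allow that to be checked.

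**What to change.** 1. **SAP 6.3.3.** Add, by arm, the number and percentage of eyes losing 3 or more Snellen lines from their own Baseline, at each scheduled visit and at any visit, including unscheduled visits where BCVA was measured. State how lines are counted.
2. **SAP 6.3.4.** Add, by arm, the number and percentage of eyes with any postoperative IOP below the protocol's hypotony cut, before 1 month and from 1 month on, using all scheduled readings and any unscheduled readings available. Reconcile protocol 3.2 (< 5 mmHg) and 9.2 (< 6 mmHg) first.
3. **High IOP, if wanted.** Label any cut as a descriptive reporting threshold. It must not be presented as a protocol limit, since the only numeric spike value applies before surgery.
4. **Cross-check.** Compare both counts with the adverse event listing, and explain eyes that meet a measured criterion without a matching event.

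The by-visit means and the rule in SAP 3.1 can otherwise stay as they are. The cost is two short tables from readings already held for the listings, plus one comparison with the adverse event data. The drawback is that unscheduled visits are irregular and need not include testing. The any-visit counts should therefore be labelled as any time observed and read as minimums, not as rates per visit.

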3.2 Baseline References

For reporting IOP results relative to ocular hypotensive medication use, two baseline references will be used as follows:

Document: TDOC-0053376 Version: 2.0; Most-Recent; Effective; CURRENT

Status: Effective

Baseline1 = The pre-surgery assessments obtained at the scheduled Screening visit
that are prior to washout (if necessary) for enrolled subjects regardless of whether the
subject is taking any ocular hypotensive medications. Also referred to as 'Medicated'
or 'Regardless of medications'.

• Baseline2 = The pre-surgery assessments obtained at the scheduled Baseline visit that are after washout of subject's ocular hypotensive medications for those subjects taking hypotensive medications; if a subject is not medicated at Screening, then Baseline2 = Baseline1 (i.e., per protocol Section 7.1, "Subjects who are medication naïve at screening may have the screening and baseline testing performed on the same day."). Also referred to as 'Unmedicated' or 'Without medications'.

All other data will reference only one baseline, designated "Baseline", defined as the last assessments obtained prior to CyPass implantation surgery on Day 0.

3.3 Prior and Concomitant Ocular Medications/Treatments

Start and stop dates of ocular medications/treatments will be compared to the date of stent implantation surgery (Day 0) to allow medications/treatments to be classified as either *prior* or *concomitant*.

All medications recorded from enrollment and prior to surgery will be classified as *prior* medications. If a medication has either (1) start date before the date of surgery and a stop date on or after the date of surgery or (2) a start date on or after the date of surgery, then the medication will be classified as *concomitant*. Concomitant medications with a start date on the date of surgery will be classified as *intraoperative* medications, while concomitant medications with a start date after surgery will be classified as *post-operative* medications.

3.4 Adverse Events

The onset date of an adverse event will be compared to the date of stent implantation surgery (Day 0) to determine if the adverse event is treatment emergent or not. Adverse events with an onset date on or after the date of surgery will be classified as treatment emergent adverse events (TEAEs). Adverse events with an onset date on the date of surgery will be classified as *intraoperative* adverse events, while adverse events with an onset date after surgery will be classified as postoperative adverse events.

Document: TDOC-0053376 Version: 2.0; Most-Recent; Effective; CURRENT

Status: Effective

3.5 Coding Dictionaries

Verbatim adverse events will be coded into internal, non-dictionary, standardized terms for presentation. Further, the relationship of each adverse event to study device or implantation procedure will be determined.

General medical and ocular histories will be categorized by body system for presentation.

4 Study Conduct and Patient Baseline Summaries

4.1 Subject Disposition

Subject accountability will be summarized per ANSI Z80.27-2014 (revision of ANSI Z80.27-2001 (R2011)), Annex G. The number and percentage of subjects enrolled in the study will be presented by site for each treatment and overall; similar tables will display the total subjects in each analysis set (e.g., FAS, Safety) by site for each treatment and overall. Finally, a table will be constructed to present the number and percentage of subjects in each of the analysis sets (i.e., FAS and Safety) by treatment and overall.

A listing of subjects discontinued from the study will also be presented and the primary reason for discontinuation will be provided for those subjects.

4.2 Protocol Deviations

A listing of protocol deviations will be provided.

4.3 Demographic and Baseline Information, and General Medical and Ophthalmic History

Demographic and baseline information will be summarized using the FAS by treatment and overall. Subject demographics include age, sex, race, and ethnicity. Baseline information includes study eye (OD, OS) and lens status (phakic, pseudophakic).

General medical history findings and ophthalmic medical/surgical history findings will be presented separately in the data listings.

4.4 Implantation Surgery and Adjunct Treatment Administration

Implantation surgery and adjunct treatment administration details will be presented in the listings.

Document: TDOC-0053376 Version: 2.0; Most-Recent; Effective; CURRENT

Status: Effective

5 Efficacy Analysis Strategy

5.1 Efficacy Endpoints

Primary Efficacy Endpoint

The outcome of \geq 20% decrease in IOP from baseline (unmedicated/Baseline2) up to 12 months post-operatively without IOP lowering medications (IOP response) is determined as follows,

Percent change in IOP from baseline is defined as, for each subject,

$$Percent \ Change = \frac{PostOperative \ IOP - Baseline \ IOP}{Baseline \ IOP} \ge 100$$

such that negative percent changes represent a favorable effect, while positive percent changes represent an unfavorable effect. Therefore, IOP response is achieved if the percent change is $\geq 20\%$ lower than baseline (i.e. the percentage change is $\leq -20\%$).

 IOP response rate: Proportion of eyes meeting the effectiveness outcome is defined as the number of eyes with occurrence of ≥ 20% decrease from baseline divided by the number of eyes having non-missing post-Baseline and Baseline IOP measurements at each the given visit.

While the IOP response rate at 12 months without IOP lowering medications is the primary endpoint, results will be summarized at each postoperative visit relative to unmedicated baseline. Note, at 12 months for subjects being treated with ocular hypotensive medications, a washout for the 12 month assessment was intended to obtain unmedicated IOP measurements. Note: prior to version D of the protocol, the 12 Month Washout visit was not required for the initial dose selection phase subjects who were on IOP lowering medication

Document: TDOC-0053376 Version: 2.0; Most-Recent; Effective; CURRENT

Status: Effective

Secondary Efficacy Endpoints

[figure not shown]
 Rate of intraoperative and post-operative device related ocular adverse events up to 12 months postoperatively

```
Rate = \frac{\text{\# of subjects who experience } either \text{ an intraoperative } and/or \text{ post} - \text{operative device related ocular AE}}{\text{\# of subjects}}
```

such that device related includes definitely, probably, or possibly.

- Mean change in medicated IOP from baseline (Baseline1) to 12 months postoperatively regardless of medications
 - Computed for subjects having both non-missing baseline medicated IOP and
 12 month postoperative regardless of medications measurements.
- Proportion of eyes using ocular hypotensive medications at 12 months postoperatively

```
\frac{Proportion}{= \frac{\# \ of \ subjects \ being \ treated \ with \ ocular \ hypotensive \ medications \ at \ the \ 12 \ month \ postoperative \ visit}{\# \ of \ subjects \ at \ the \ 12 \ month \ postoperative \ visit}}
```

[figure not shown]

Document: TDOC-0053376 Version: 2.0; Most-Recent; Effective; CURRENT

Status: Effective

A data listing will accompany this summary presenting each subject's Screening, Baseline, 6 month, and 12 month (regardless of medications and/or unmedicated) IOP measurements, number of IOP medications, and corresponding aqueous lake characteristics, where applicable.

Document: TDOC-0053376 Version: 2.0; Most-Recent; Effective; CURRENT

Status: Effective

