2.1 Full Analysis Set

The full analysis set (FAS) will serve as the primary set for the efficacy analyses. The FAS includes all randomized subjects who undergo CyPass implantation surgery.

All primary and secondary endpoint summaries will be carried out using the FAS analysis set; that is, subjects assigned to the treatment to which they were randomized.

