5.3 Statistical Methods for Efficacy Analyses

The primary efficacy endpoint, the achievement of a 20% decrease in IOP relative to baseline in the absence of IOP lowering medications up to 12 months post-operatively will be summarized at each post-operative visit by the number and percent of subjects having IOP response and the corresponding 95% confidence interval (CI) based on the exact binomial distribution.

[figure not shown]
Secondary efficacy endpoints describing proportions meeting given criteria will be summarized at each post-operative visit by the number and percentage of responses and the corresponding 95% CI based on the exact binomial distribution. While descriptive statistics for all continuous parameters for the actual values and change from baseline, including the 95% CI of the actual/observed results (based on a *t*-distribution) and change (based on a paired *t*-distribution), will be provided for each protocol specified visit, the 12 month visit is of most interest.

All efficacy analysis summaries will be produced using the FAS set.

Document: TDOC-0053376 Version: 2.0; Most-Recent; Effective; CURRENT

Status: Effective

Document: TDOC-0053376 Version: 2.0; Most-Recent; Effective; CURRENT

Status: Effective

6 Safety Analysis Strategy

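### The visible primary responder rule makes no provision for a secondary IOP-lowering surgical or laser procedure; state the strategy and add one supplementary analysis (minor)

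*SAP*

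**What the plan says.** SAP 5.1 computes each eye's percent change from the unmedicated baseline (Baseline2) and states that "IOP response is achieved if the percent change is" at or below minus 20%. The response rate is taken over the "number of eyes having non-missing post-Baseline and Baseline IOP measurements" at the visit in question. Protocol 2.4, 5.1, 8.1 and 8.3, and SAP 5.3 and 7, restate the endpoint in terms of pressure and medication only.

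On medication the plan is explicit. For eyes under treatment at 12 months, "a washout for the 12 month assessment was intended to obtain unmedicated IOP measurements".

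On who is counted, SAP 2.1 says: "The FAS includes all randomized subjects who undergo CyPass implantation surgery". No one is removed for a later procedure. SAP 3.1 adds: "No imputations will be made for missing data". SAP 5.3 reports each visit's responder count and percentage with the "corresponding 95% confidence interval (CI) based on the exact binomial distribution".

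The protocol foresees further intervention. Section 9.2 lists "Significant elevation in IOP requiring non-medical intervention" among the anticipated postoperative events, along with unplanned ocular reoperation. In the visible SAP, secondary surgery appears only in safety outputs, chiefly the listing in 6.3.9 with surgery term and date. Explantation and repositioning are listed in 6.3.10.

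**The concern.** The endpoint is built to separate the implant's effect from other IOP-lowering treatment: medication is excluded by definition and washed out at Month 12. A second IOP-lowering procedure also lowers pressure, but it cannot be washed out. Before surgery, protocol 7.1 treats restarted medication and surgical intervention alike, since either takes the subject out of the study. After surgery, the visible responder rule deals only with medication.

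Such an eye can have a Month 12 value. Protocol 7.6.1 does not name a second procedure as a reason for exit and asks that implanted subjects who are terminated still be followed for safety. SAP 6.1 and 6.3.4 make IOP part of the safety assessments. The eye can therefore be credited as a success of the first implantation, or drop out if unmeasured. In neither case does needing another procedure count against it. At stake is what the per-arm response rate means.

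**Working it through.** **1. The plan's own figure.** Inputs from SAP 7: 30% control, 60% visco-assisted, two-sided alpha 0.05, likelihood ratio chi-square test, 43 eyes per arm, 80% power. With H(p) = p ln p + (1 - p) ln(1 - p), the noncentrality is 2n[H(0.30) + H(0.60) - 2H(0.45)]. At n = 43 this is 86 x 0.0924 = 7.95, which gives power 80.5%; n = 42 gives 79.6%. The stated 43 per arm reproduces, and this point does not alter it.

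**2. What the rule does with an eye that had a second IOP-lowering procedure.**

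- Measured off medication and at least 20% down: responder.
- Measured and not 20% down: non-responder.
- No Month 12 IOP: out of numerator and denominator.

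**3. Illustration: measured eyes counted as responders.** The counts of such eyes are assumed; the documents give none. One eye moves an arm by 1/43 = 2.3 points and four by 4/43 = 9.3 points. The nearest whole-eye counts to the planning rates are 13/43 and 26/43. Intervals are exact binomial (Clopper-Pearson) 95%.

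| Assumed case | Control | Visco-assisted | Difference (points) |
|---|---|---|---|
| Such eyes counted as failures | 13/43 = 30.2% (17.2 to 46.1) | 26/43 = 60.5% (44.4 to 75.0) | 30.2 |
| Two counted as responders in each arm | 15/43 = 34.9% (21.0 to 50.9) | 28/43 = 65.1% (49.1 to 79.0) | 30.2 |
| Two in control only | 15/43 = 34.9% | 26/43 = 60.5% | 25.6 |
| Two in visco-assisted only | 13/43 = 30.2% | 28/43 = 65.1% | 34.9 |

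**4. Illustration: such eyes with missing IOP.** These lie outside the 43. SAP 7 plans 101 enrolled and 86 completing, so 101 - 86 = 15 eyes, or 7 to 8 per arm, are not measured at Month 12 for any reason. Restoring one as a failure lowers control by 13/43 - 13/44 = 0.7 points and visco-assisted by 26/43 - 26/44 = 1.4 points.

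| Two restored as failures in | Control | Visco-assisted | Difference (points) |
|---|---|---|---|
| Both arms | 13/45 = 28.9% (16.4 to 44.3) | 26/45 = 57.8% (42.2 to 72.3) | 28.9 |
| Control only | 13/45 = 28.9% | 26/43 = 60.5% | 31.6 |
| Visco-assisted only | 13/43 = 30.2% | 26/45 = 57.8% | 27.5 |

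**5. Reading.** Counting these eyes as failures can lower an arm's rate or leave it unchanged. The between-arm difference can stay, narrow or widen. With one or two eyes, the shifts are small beside intervals about 28 to 31 points wide.

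**The case against.** The strongest objection is that the rule is unlabelled rather than wrong. Using observed pressure whatever happened later is a recognised strategy, and the full analysis set, the non-missing denominator and the ban on imputation together amount to that. This stands, and it is why the rule need not be replaced.

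Second, parts of SAP section 5 are not visible, and the SAP follows protocol Version F while the protocol supplied is Version D. A provision may exist out of sight. This also stands, and limits the point to the visible text.

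Third, nothing shows that such procedures are common. Protocol 6.2 excludes advanced glaucoma and eyes with a known condition that may need intraocular intervention, sections 7.4.1 and 7.4.2 allow medication for raised pressure, and 9.2 is only a list of anticipated events. Affected eyes can also be traced by hand, because SAP 6.3.9 lists the surgery and a subject-level listing in section 5 gives Month 12 IOP. That makes the issue visible but does not yield a response rate.

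Fourth, counting such eyes as failures has its own defects. Scoring an unmeasured eye is imputation, which SAP 3.1 rules out. SAP 1.4 says that the study was not masked, so the decision to reoperate could shape the outcome. The exemption in protocol 9.2, "other than paracentesis to relieve pressure prior to 1 week postoperative", belongs to an adverse-event definition and is not an efficacy rule. These objections argue against a new primary rule and for a disclosed supplementary analysis.

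A reader might go further and infer that the treatment effect is inflated or power is lost. If an extra 5% or 10% of control eyes alone (about 2 or 4 of 43) were counted as responders, power by the usual two-proportion formula would fall from 81% to 65% or 46%. The documents do not support that inference. Those shares are assumed, equal shares leave the difference at 30 points and power at about 81%, and the visible primary analysis is a per-arm rate with an interval.

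**Conclusion.** The point holds as a minor one. In the visible text, a Month 12 responder is defined by pressure and medication alone, so a per-arm response rate can include an effect of a later IOP-lowering procedure, and an eye with such a procedure and no Month 12 pressure is dropped. Each such eye counted as a responder is worth 2.3 points in an arm of 43; each missing eye restored as a failure is worth 0.7 points (control) or 1.4 points (visco-assisted) at the planning rates. The number of such eyes, their split by arm and the direction of any change in the difference are unknown.

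Two stronger conclusions are not supported: that the primary rule must be replaced, and that the comparison is biased in a known direction. The first would depart from the endpoint as the protocol defines it, late in an unmasked study whose Cohort 1 efficacy data had already been reviewed. The second needs a rate of second procedures by arm, which the documents do not give. Confidence is moderate because of the parts not shown and the difference in protocol version.

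**What to change.** - **SAP 5.1.** Keep the protocol-defined rule as primary, and state that it uses observed IOP regardless of later procedures.
- **Supplementary analysis.** Prespecify one, reported beside the primary result with exact 95% intervals. An eye with a secondary IOP-lowering surgical or laser procedure on or before a visit is a non-responder at that and later visits, and stays in the denominator even if its IOP is missing.
- **SAP 3.1.** Record this as an explicit exception to the no-imputation statement.
- **Classification.** Sort the surgery terms listed under SAP 6.3.9 into IOP-lowering or not, without sight of arm or IOP. List any paracentesis, and show the result with and without counting it.
- **Reporting.** Give the number of such eyes per arm, and date and disclose the addition.

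If a part of section 5 that is not visible already contains such a rule, cross-refer to it from 5.1 instead.

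The cost is a few sentences, one classification from data already listed, and one more table. Response rates in that analysis will be slightly lower if any such eyes exist. Because the study is unmasked, the decision to reoperate can itself influence the supplementary result, and the report should say so.
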